Protocol Synopsis

Name of Sponsor: Korea Otsuka Pharmaceutical Co., Ltd.	Protocol#
Name of Investigational Medicinal Product: Samsca [®] Tablets	156-KOA-1201n
Protocol Title:	Post Marketing Surveillance Study of Safety and Efficacy of Samsca [®] Tablets under the "New Drug Re-Examination"
Clinical Phase:	Post Marketing Surveillance
Treatment Indication:	The treatment of clinically significant hypervolemic and euvolemic hyponatremia [serum sodium < 125 mEq/L or hyponatremia that is symptomatic and has resisted correction with fluid restriction], including patients with heart failure, and Syndrome of Inappropriate Antidiuretic Hormone (SIADH) and etc.
Objective(s):	
The objective of this study is to evaluate following items in relation with use of Samsca[®] in normal medical practice;
 
 1. Serious adverse event and adverse drug reaction profile 2. Unexpected adverse event/adverse drug reaction profile 3. Known adverse drug reaction profile 4. Non-serious adverse drug reaction profile 5. Other information related to the product safety and efficacy 
The hypothesis of this study is that Samsca[®] is safe and efficacious in the treatment.

Trial Design:	
This is a Post-Marketing Surveillance study of Samsca[®] tablets in accordance with Korean regulations on New Drug Re-examination (i.e. New Drug Re-examination Standards: MFDS Notification No. 2015-79 dated 30Oct2015). This study will be conducted in a prospective, single-arm, multi-center format. As this study is observational in nature, the patient's follow-up is not prescriptive in nature and must be left up to the judgment of the physician (investigator), within the period of observation set forth in the protocol.
 
The protocol will be developed in accordance with the MFDS guideline.
 
*MFDS : Ministry of Food and Drug Safety

Trial Population:	
At least 3000 patients will be enrolled for surveillance to meet the local regulatory requirements. About 100~150 investigators across the country will be participating in this surveillance and the number of patients to be enrolled by each investigator will vary.

**Inclusion/Exclusion
Criteria:**

Inclusion Criteria

Subjects must meet all of the following inclusion criteria to be eligible for enrollment into the study :

Efficacy Measures:	
1. The change of serum sodium level from baseline to end of treatment period or discharge for a given hyponatremia treatment: Efficacy measurement covers a maximum of 4 days.
 
2. Overall judgement
 
Holistically judge it according to the judgement of serum sodium level and clinical symptoms: Effective, No effect, Worsen

Statistical Methods:
	
Safety analysis set includes all subjects who received Samsca[®] tablets at least once and followed up for the safety evaluation. Efficacy analysis set includes all subjects who received Samsca[®] tablets and efficacy evaluation data is available.
 
In interim reports, the descriptive statistics for continuous variables and frequency (n) and percentage (%) for categorical variables will be presented in overall patients.
 
In final report (Re-examination report), safety and efficacy measures will be summarized and analyzed in overall patients and by background factors.
 
For continuous variables, the descriptive statistics will be presented, and the analysis will be performed using the analysis of covariance (ANCOVA) model with background as a factor and baseline serum sodium level as a covariate.
 
For categorical variables, frequency (n) and percentage (%) will be presented, and the analysis will be performed using Chi-square test or Fisher's exact test between categories of background factors. Also, 95% confidence interval of incidence rate of adverse event will be described.
 
Data for special population (i.e. pregnant women, elderly patients, patients with liver or renal disease) will be presented as well.

Estimated Duration of study
	
Planned study schedule as per local regulation is as below;
 
 1. Regulatory approval on Samsca[®]: September 2011 2. Product launch date: December 2012 3. Study period: September 2011 – August 2017 4. Interim reports to MFDS: every 6 months for first 2 years, then annually thereafter. 5. Final report to MFDS: within 3 months of study completion

[Appendix]

Management and reporting of safety information

Collection period of safety information is after first use of Otsuka product until 2 days after discontinuation RESEARCHER shall submit to OTSUKA any SAFETY EVENT within the following timeline:

- (a) Twenty-four (24) hours from RESEARCHER’s receipt of SAFETY EVENT classified as serious adverse event and non-serious adverse event (defined below) or Product Quality Complaint (PQC) or Pregnancy;
- (b) For all other safety information as defined above and not specified in (a), RESEARCHER shall send the line-listing to OTSUKA at the end of each study, or during the study upon OTSUKA’s request.

Procedures for the collection, management and reporting of individual cases of safety information while the study is being conducted, and for the periodic and end of study reconciliation of serious/non-serious adverse events between PV database and study database, aligned with the current version of G-SOP-ALL-007. Safety data reconciliation will be conducted comparing the safety database and the clinical database when study report (annual report& re-examination report) is submitted. The detail of reconciliation including frequency will be described in the Data Management Plan (DMP).

Below is the definition of Safety information including Adverse Event(AE), Serious Adverse Event(SAE), Non-Serious Adverse Event(NSAE).

Safety information	Safety Information as below will be reported in accordance with the current Otsuka Global GxP/Pharmacovigilance Glossary. “Any information from any source containing information including 
- Adverse event or suspension thereof- Lack of efficacy- Overdose/incorrect dosage (accidental or intentional)- Abuse/misuse (e.g., patients sharing medication) – even without resulting adverse reaction- Accidental exposure (e.g., child takes parent’s medication)- Medication error
--------------------	--

	
 - Withdrawal reactions - Disease progression/exacerbation of existing disease - Drug-drug/Drug-food interactions - Exposure to drug during pregnancy, where the embryo or fetus may have been exposed to medicinal products (either through maternal exposure or transmission of a medicinal product via semen following paternal exposure) - Exposure to drug during lactation (including uneventful) - Suspected counterfeit product - Suspected transfer of infectious disease/agent by the medicinal product concerned - Product Quality Complaint (PQC) with safety related/medically important information - Pediatric use (if not an approved use) - Occupational exposure - Off-label use
Adverse Event (AE)	
Any untoward medicinal occurrence in a patient or clinical study subject administered a medicinal product and which does not necessarily have a causal relationship with this treatment (Directive 2001/83/EC amended by Directive 2010/84/ EU).
 
An adverse event can therefore be any unfavorable and unintended sign (e.g. abnormal laboratory finding), symptom, or disease temporally associated with the use of a medicinal product, whether or not it is considered causally related to the medicinal product.

Serious Adverse Event (SAE)	
Any adverse drug experience/event occurring at any dose which
 
 - results in death, - is life-threatening, - requires inpatient hospitalization or prolonged of existing hospitalization, - results in persistent or significant disability or incapacity, - is a congenital anomaly/birth defect,

	
- is medically significant
 
Life-threatening refers to an event in which the patient was at risk of death at the time of the event; it does not refer to an event that hypothetically might have caused death if more severe.
 
A medically significant event is an important medical event (defined as a medical event(s) that may not be immediately life-threatening or result in death or hospitalization but, based on appropriate medical and scientific judgment, may jeopardize the patient/subject or may require intervention (e.g. medical, surgical) to prevent one of the other outcomes listed in the definition above) might be considered serious as well, examples of such include, but not limited to, intensive treatment in an emergency room or at home for allergic bronchospasm; blood dyscrasias; or convulsions that do not result in hospitalization; or development of drug dependency of drug abuse.

Non-serious Adverse Event	All Adverse Events that do not meet the definition of a Serious Adverse Event are considered Non-serious Adverse Events.

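### By-factor tests in the final report are unadjusted: they describe differences between patient groups but cannot show which of several overlapping factors carries a difference; a supplementary joint model would be a cheap improvement

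*Combined protocol and SAP*

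**What the plan says.** The analysis plan is the Statistical Methods row of the Protocol Synopsis. In the final report, "safety and efficacy measures will be summarized and analyzed in overall patients and by background factors".

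- **Categorical outcomes** get counts, percentages and a Chi-square or Fisher's "exact test between categories of background factors". This covers the incidence of adverse events, adverse drug reactions and serious adverse events. A 95% confidence interval is planned for adverse event incidence.
- **Continuous outcomes**, in practice the change in serum sodium, get an ANCOVA "model with background as a factor and baseline serum sodium level as a covariate".
- **Special populations** are to be presented as well: "pregnant women, elderly patients, patients with liver or renal disease". The text does not say that these groups are tested.

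Elsewhere in the Synopsis, the indication covers euvolemic and hypervolemic hyponatremia, "including patients with heart failure, and Syndrome of Inappropriate Antidiuretic Hormone (SIADH) and etc". The design is stated as "This study will be conducted in a prospective, single-arm, multi-center format", and the size as "At least 3000 patients will be enrolled for surveillance to meet the local regulatory requirements".

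The text does not list the background factors, give a significance level for the by-factor tests, or say how a significant factor will be interpreted. It contains no multivariable model and no stratified test.

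**The concern.** There is no comparator arm, so the by-factor comparisons are the only planned inference about which patients fare worse. Background factors are not randomised, and several that the Synopsis mentions (older age, heart failure, liver or renal disease) may well occur together. A Chi-square or Fisher test carries no covariate. If elderly patients have more heart failure, and heart failure raises event risk, the age table shows a difference even when age adds nothing once heart failure is known. The reverse can also happen: if two factors run in opposite directions, a factor that matters can show almost no crude difference.

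At stake is how the by-factor tables are read. A significant test on age, with nothing beside it, is easily taken to mean that age itself raises the risk. The plan offers no analysis that could confirm or correct that reading. The overall incidence and its confidence interval are not affected.

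**Working it through.** **No figure to reproduce.** The 3000 is a regulatory minimum. The documents give no event rate, effect size, power or alpha for these tests, so the size of the issue can only be illustrated.

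**Inputs.** From the Synopsis: N = 3000, and an unadjusted test between categories. Assumed: 1500 elderly and 1500 younger patients; event risk 20% with heart failure and 10% without; no age effect given heart failure; two-sided alpha 0.05; heart failure prevalence *a1* in the elderly and *a0* in the younger.

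**Formulas.** The marginal risk in an age group is 0.10 + 0.10 × prevalence. With p̄ the mean of the two risks, the standard error under equality is √[2p̄(1 − p̄)/1500], and the expected z is the difference divided by that standard error. The chance of a significant test is about Φ(z − 1.96), as the other tail and the change in variance are negligible here.

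**Middle scenario in full (50% vs 25%).** Risks are 0.10 + 0.10 × 0.50 = 15.0% and 0.10 + 0.10 × 0.25 = 12.5%. p̄ = 0.1375, so SE = √(2 × 0.1375 × 0.8625/1500) = 0.01257. Then z = 0.025/0.01257 = 1.99, and Φ(0.03) ≈ 51%.

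| Heart failure, elderly vs younger | Marginal risks | Expected z | Crude test flags age (formula) | Crude, simulated | Stratified by heart failure, simulated |
|---|---|---|---|---|---|
| 40% vs 30% | 14.0% vs 13.0% | 0.80 | 13% | 12% | 5% |
| 50% vs 25% | 15.0% vs 12.5% | 1.99 | 51% | 51% | 5% |
| 60% vs 20% | 16.0% vs 12.0% | 3.16 | 88% | 89% | 5% |

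The simulation used 20,000 studies per row and a Mantel-Haenszel test for the last column. In the 40% vs 30% row the formula figure includes the small second tail.

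**Sensitivity to the assumptions.** Take instead a true factor present in 20% of patients without the other factor.

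- Base risk 10%, risk ratio 2: with the true factor in 30%, 40% or 50% of those with the other factor, the no-effect factor is flagged in 13%, 37% or 67% of studies.
- Base risk 20%, risk ratio 2, 50% vs 20%: 96%.
- Base risk 5%, risk ratio 1.5, 30% vs 20%: the risks are 5.75% vs 5.50%, and the rate is about 6%, close to nominal.

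**Masking.** Suppose age does raise risk (risk ratio 1.25), but heart failure is in 25% of elderly and 50% of younger patients. Crude risks are 1.25 × (0.10 + 0.10 × 0.25) = 15.6% and 0.10 + 0.10 × 0.50 = 15.0%. The crude test detects age in about 8% of simulated studies, the stratified test in about 71%.

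**What these rates are.** In every row of the table the two age groups really do differ in incidence. The crude test is therefore detecting a true marginal difference. The last column answers a different question: whether age adds anything once heart failure is known. The gap between the columns measures how far the two questions diverge; it is not a false-positive rate of the planned test.

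**Sodium change.** No calculation was made for the ANCOVA. The wording refers to background in the singular and names baseline sodium as the only covariate, which suggests one factor per model. That is a reading of a terse sentence, not an explicit statement.

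**The case against.** The strongest reply is that the plan asks a marginal question and answers it correctly. The objectives are event profiles in normal practice. A prescriber wants to know how often events occur in elderly patients as they present, with their comorbidities, and 15.0% vs 12.5% is then the right answer. This stands.

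A reader might infer that the planned tests have an inflated type I error, or that the sponsor will name the wrong risk factor. The documents support neither. The null hypothesis of a Chi-square test between age categories is equal incidence in those categories, and in the illustration that null is false. Nowhere does the text promise to identify independent or causal risk factors.

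Three further points stand. The background factors are not listed and their correlation is not documented, so the size of the problem is unknown and could be negligible. The supplied text is a synopsis with a safety appendix, so a fuller analysis plan may exist that covers this. And a joint model has its own limit: if age leads to heart failure or renal disease, adjusting for these removes part of the age association. Resting every statement about risk on adjusted results could hide a true excess in the elderly.

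What the reply does not remove is that the plan goes beyond tabulation. It adds significance tests without saying how a significant factor is to be read, and offers nothing to separate factors that overlap.

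**Conclusion.** The point holds as a cheap improvement, not as an error in the plan. On the supplied text, the by-factor tests of categorical outcomes are unadjusted, and the sodium ANCOVA appears to take one background factor at a time. The tests describe marginal differences validly. They cannot attribute a difference to one of several overlapping factors.

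Under the assumed heart failure example, the unadjusted test flags age in about 13% to 89% of studies, against about 5% with stratification. Other plausible inputs widen this to about 6% to 96%. The low end is weak correlation with a small effect, where adjustment would change little. All these figures rest on assumed prevalences, risks and risk ratios, and on an assumed alpha of 0.05. That the plan is unadjusted does not depend on them; the practical importance does.

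**What to change.** 1. List the background factors in advance.
2. Keep the crude tables and the Chi-square or Fisher tests, labelled as unadjusted and exploratory.
3. Add one supplementary multivariable logistic model each for adverse events, adverse drug reactions and serious adverse events, with the listed factors together (for example age, sex, underlying disease, liver disease, renal disease). Use a penalised fit if events are sparse.
4. Add one ANCOVA of sodium change with the same factors together plus baseline sodium.
5. Show adjusted odds ratios or differences with 95% confidence intervals beside the crude results.
6. State the rule of interpretation: claims of independent association rest on the adjusted results; statements about incidence in a patient group rest on the crude results.

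The cost is some analysis-plan wording and four models. It needs no new patients or visits, provided the listed factors are already recorded. The downsides are loss of patients with missing factor values in a complete-case model, wide intervals for rare outcomes, and an adjusted age effect that excludes whatever acts through comorbidity. The last should be stated in the report.
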